4.1 Investigational Product

An investigational product, also known as investigational medicinal product in some regions, is defined a pharmaceutical form of an active substance or placebo being tested or used as a reference in a clinical study, including products already with a marketing authorization but used or assembled (formulated or packaged) differently than the authorized form, or used for an unauthorized indication, or when used to gain further information about the authorized form.

The investigational product should be stored in a secure area according to local regulations. It is the responsibility of the investigator to ensure that investigational product is only dispensed to study subjects. The investigational product must be dispensed only from official study sites by authorized personnel according to local regulations.

In this protocol, investigational product(s) is/are: BMS-955176, ATV, and DTG (in countries where DTG has not been approved for use). These products will be supplied.

4.2 Non-investigational Product

Other medications used as support or escape medication for preventative, diagnostic, or therapeutic reasons, as components of the standard of care for a given diagnosis, may be considered as non-investigational products.

In this protocol, noninvestigational product(s) is/are: TDF, RTV, and DTG (in countries where DTG is approved for use). These products will be supplied.

4.3 Storage and Dispensing

The product storage manager should ensure that the study drug is stored in accordance with the environmental conditions (temperature, light, and humidity) as determined by BMS. If concerns regarding the quality or appearance of the study drug arise, the study drug should not be dispensed and contact BMS immediately.

Study drug not supplied by BMS will be stored in accordance with the package insert.

Investigational product documentation (whether supplied by BMS or not) must be maintained that includes all processes required to ensure drug is accurately administered. This includes documentation of drug storage, administration and, as applicable, storage temperatures, reconstitution, and use of required processes (eg, required diluents, administration sets).

Storage facilities for controlled substances must be securely locked and substantially constructed, with restricted access to prevent theft or diversion, as applicable by local regulations.

4.4 Method of Assigning Subject Identification

At the start of the screening period, the investigative staff will call the Assignment Center via an Interactive Voice Response System ([IVRS], or its web-based equivalent) designated by the sponsor to enroll the subject and to obtain a subject patient identification number (PID).

For subjects who meet the protocol eligibility criteria, the investigative staff will call the IVRS and subjects will start treatment.

Subjects will be randomly assigned in the staged fashion to one of the treatment arms, and stratified by HIV-1 Clade (AE versus Other), as described in [Section 3](#) and as outlined in the AI468048 Study Schematic [Figure 3.1.6-1](#).

Note: All efforts should be made to limit the possibility of randomizing subjects that do not start treatment. If a subject is randomized but does not receive study medication, the BMS study team must be notified immediately.

4.5 Selection and Timing of Dose for Each Subject

Subjects will be randomized into the treatment arms in a staged fashion described in [Section 3.1](#).

Stage 1:

In Stage 1, subjects will be randomly assigned 1:1 to one of two treatment arms and on Day 1 will begin dosing with:

- Arm 1 : BMS-955176 120 mg QD + ATV/r 300/100 mg QD + DTG 50 mg QD, or
- Arm 2: TDF 300 mg QD + ATV/r 300/100 mg QD + DTG 50 mg QD

Stage 2:

In Stage 2, subjects will be randomly assigned 1:1:1 to one of three treatment arms and on Day 1 will begin dosing with:

- Arm 3: BMS-955176 120 mg QD + ATV 400 mg QD + DTG 50 mg QD, or
- Arm 4: BMS-955176 180 mg QD + ATV 400 mg QD + DTG 50 mg QD, or
- Arm 5: TDF 300 mg QD + ATV/r 300/100 mg QD + DTG 50 mg QD

4.5.1 Instructions for Dose Administration

4.5.1.1 General Instructions

- Subjects should administer doses of each drug from only one bottle at a time, until that bottle is empty, before another bottle may be opened.
- Subjects will be required to complete Dosing Diaries so that drug administration can be accurately accounted. It is important that sites provide instructions to subjects for completion and obtain their acknowledgment that doing so provides critical information for the clinical trial.
- Dosing times (and study appointment times) must be carefully considered through Week 24 due to the requirements of the PK collection outlined in [Section 5.5](#).

4.5.1.2 Specific Dosing Instructions for Initial Treatment Arm Assignment

In the morning, with a meal, subjects will take the following:

- Arm 1: One pill each from bottles BMS-955176 120 mg, ATV, RTV, and DTG
- Arm 2: One pill each from bottles TDF, ATV, RTV and DTG

- Arm 3: One pill each from bottles BMS-955176 120 mg, DTG, and two pills from bottle ATV (the unboosted dose of ATV is 400 mg, achieved by 200 mg x 2)
- Arm 4: One pill each from bottles BMS-955176 60 mg, BMS-955176 120 mg and DTG, and two pills from bottle ATV (the unboosted dose of ATV is 400 mg, achieved by 200 mg x 2)
- Arm 5: One pill each from bottles TDF, ATV, RTV and DTG

4.5.2 Dose Modifications

No dose adjustments or changes in intake frequency are allowed for any of the assigned study drugs in the protocol, except for the unique case of treatment-limiting renal toxicity which limits the use of the TDF. In the event of treatment-limiting renal toxicity, dose interval adjustments for TDF are permitted according to the local package insert/label, and only after the completion of the Week 2 Intensive PK optional Visit, if the subject is inclined to participate.

4.6 Blinding/Unblinding

Not applicable.

4.7 Treatment Compliance

Treatment Adherence to the treatment regimen will be critical to the conduct of this study. Adherence will be evaluated by the investigative staff at every treatment visit (including telephone contact visits) through interviews with the subjects and through examination of returned medication. It is expected that site staff attempt to have subjects maintain 90% treatment compliance or greater. Subjects should be instructed to bring all unused study medication back in the original container to each visit. Site staff are required to review Dosing Diaries completed by the subject, and to reinforce their use.

4.8 Destruction of Study Drug

For this study, study drugs (those supplied by BMS or sourced by the investigator) such as partially used study drug containers, vials and syringes may be destroyed on site.

Any unused study drugs can only be destroyed after being inspected and reconciled by the responsible Study Monitor unless study drug containers must be immediately destroyed as required for safety, or to meet local regulations (eg, cytotoxics or biologics).

On-site destruction is allowed provided the following minimal standards are met:

- On-site disposal practices must not expose humans to risks from the drug
- On-site disposal practices and procedures are in agreement with applicable laws and regulations, including any special requirements for controlled or hazardous substances
- Written procedures for on-site disposal are available and followed. The procedures must be filed with the site's SOPs and a copy provided to BMS upon request

- Records are maintained that allow for traceability of each container, including the date disposed of, quantity disposed, and identification of the person disposing the containers. The method of disposal, ie, incinerator, licensed sanitary landfill, or licensed waste disposal vendor must be documented
- Accountability and disposal records are complete, up-to-date, and available for the Monitor to review throughout the clinical trial period

If conditions for destruction cannot be met the responsible Study Monitor will make arrangements for return of study drug.

It is the investigator's responsibility to arrange for disposal of all empty containers, provided that procedures for proper disposal have been established according to applicable federal, state, local, and institutional guidelines and procedures, and provided that appropriate records of disposal are kept.

4.9 Return of Study Drug

If study drug will not be destroyed upon completion or termination of the study, all unused and/or partially used study drug that was supplied by BMS must be returned to BMS. The return of study drug will be arranged by the responsible Study Monitor.

It is the investigator's responsibility to arrange for disposal of all empty containers, provided that procedures for proper disposal have been established according to applicable federal, state, local, and institutional guidelines and procedures, and provided that appropriate records of disposal are kept.

5 STUDY ASSESSMENTS AND PROCEDURES

5.1 Flow Chart/Time and Events Schedule

Table 5.1-1: Screening Procedural Outline (AI468048)

Procedure	Screening Visit (42-day screening period)	Notes
Eligibility Assessments		
Informed Consent	X	
Call IVRS to Enroll the subject; PID assigned	X	
Inclusion/Exclusion Criteria	X	
Medical History	X	Includes historical CDC Class C Events
Non-Laboratory Safety Assessments		
Full Physical Examination	X	See Section 5.3.1 for requirements
Vital Signs & Physical Measurements	X	See Section 5.3.1 for requirements
Pre-treatment events	X	Only CDC Class C events with onset during the Screening period
Serious Adverse Events Assessment	X	All SAEs that occur after the ICF has been signed should be reported
ECG	X	See Section 5.3.4 for requirements
Pregnancy Test	X	WOCBP For females under age 55, an FSH level must be on record to confirm she is not a WOCBP if pregnancy testing is not being performed. If positive urine, request serum hCG quant. on lab requisition.
Laboratory Assessments		
Fasting Chemistry and Lipid Panel	X	Fasting overnight
Hematology	X	
Urinalysis	X	
Plasma HIV-1 RNA	X	This is the confirmatory HIV-1 RNA (The first value is provided by the PI)

Table 5.1-1: Screening Procedural Outline (AI468048)

Procedure	Screening Visit (42-day screening period)	Notes
CD4+ and CD8+ T-cell count	X	
HBV Surface Antigen	X	
HCV Serology	X	
Urine toxicology (drugs of abuse)	X	Could aid in the selection of appropriate study candidates.
Pharmacodiagnostic (PDx) sample ^a	X	Plasma collection to be banked for potential future use in development of novel predictive assay(s)
Resistance Testing (HIV-1 Drug Resistance)		
PhenoSense GT Plus Integrase	X	Complete set of test results may take up to 4 weeks.
PhenoSense Gag	X	
Next Generation Seq. - Qs Gag	X	
Exploratory Resistance (HIV-1 Drug Resistance)	X	Molecular analysis at BMS WFD Discovery of baseline resistant samples and baseline sensitive controls in cases of subsequent on-treatment virologic failure

^a By definition, a pharmacodiagnostic sample (PDx) is a pre-treatment test to determine whether or not a patient is likely to respond to a drug (ie, a predictive test). Based on the results of clinical studies with BMS-955176, BMS may have to develop a PDx assay. Thus, PDx samples obtained at Screening in this study would be used for that sole purpose.

Table 5.1-2: Short-term Procedural Outline (AI468048)

Procedure	In-clinic Visit Day 1	In-Clinic Visit Optional Week 2 for Intensive PK (Day 12-16)	In-Clinic Visits Weeks 4, 8, 12, 16, 24, 32, 40, 48, 60, 72, 84, 96, and/or Early Termination (ET) (± 5 days)	Phone Visits Weeks 20, 28, 36, 44, 54, 66, 78, 90 (± 5 days)	Notes
Eligibility Assessments					
Inclusion/Exclusion Criteria	X				
Non-Laboratory Safety Assessments					
Full Physical Examination			WK 12, 24, 48, 96/ET		See Section 5.3.1 for requirements
Targeted Physical Examination	X		WK 4, 8, 16, 32, 40, 60, 72, 84		See Section 5.3.1 for requirements
Vital Signs & Physical Measurements	X		X		See Section 5.3.1 for requirements
Adherence Assessments			X	X	Including review of Dosing Diaries
Pre-treatment Events	X				See Table 5.1-1
Adverse Events Assessments	X	X	X		Serious and Non-serious AEs
Concomitant Medications	X	X	X		See Section 5.3.3
ECG	X		WK 4, 12, 24, 48, 96/ET		See Section 5.3.4 for requirements
Pregnancy Test	X	X	X		For females under age 55, an FSH level must be on record to confirm she is not a WOCBP if pregnancy testing is not being performed. If positive urine, request serum hCG quant. on lab requisition.

Table 5.1-2: Short-term Procedural Outline (AI468048)

Procedure	In-clinic Visit Day 1	In-Clinic Visit Optional Week 2 for Intensive PK (Day 12-16)	In-Clinic Visits Weeks 4, 8, 12, 16, 24, 32, 40, 48, 60, 72, 84, 96, and/or Early Termination (ET) (± 5 days)	Phone Visits Weeks 20, 28, 36, 44, 54, 66, 78, 90 (± 5 days)	Notes
Provide WOCBP with Home Pregnancy test kit(s) to be used during the in-clinic visit interval			WK 16, 24, 32, 40, 48, 60, 72, 84		Provide One Kit at Weeks 16 - 40 Provide Two Kits at Weeks 48 - 84 WOCBP subjects perform test Q4 weeks at home and report results to site.
Laboratory Assessments for Safety and Efficacy and Other Endpoints					
Fasting Chemistry	X		X		Fasting overnight
Fasting Lipid Panel	X		WK 4, 12, 24, 48, 96/ET		Fasting overnight
Hematology	X		X		
Urinalysis	X		X		
Fractional Excretion of Phosphorous (FePO4) (Urine creatinine and phosphorus, Plasma creatinine and phosphorus)	X		WK 48 and 96/ET		
Plasma HIV-1 RNA	X	X	X		If collecting an HIV-1 RNA at an UNSCHEDULED visit, also collect samples for Resistance and Exploratory Resistance Testing
CD4 and CD8 T-cell counts	X		X		
HBV Surface Antigen			WK 48 and 96/ET		
HCV Serology			WK 48 and 96/ET		Positive HCV Ab will reflex to HCV RNA

Table 5.1-2: Short-term Procedural Outline (AI468048)

Procedure	In-clinic Visit Day 1	In-Clinic Visit Optional Week 2 for Intensive PK (Day 12-16)	In-Clinic Visits Weeks 4, 8, 12, 16, 24, 32, 40, 48, 60, 72, 84, 96, and/or Early Termination (ET) (± 5 days)	Phone Visits Weeks 20, 28, 36, 44, 54, 66, 78, 90 (± 5 days)	Notes
Resistance Testing (HIV-1 Drug Resistance)					
PhenoSense GT Plus Integrase	X		X		Samples stored and tested if needed (ie, analyses of subjects if deemed clinically relevant) See Section 5.4.2.2
PhenoSense Gag	X		X		
Next Generation Seq. - Qs Gag	X		X		
Exploratory Resistance (HIV-1 Drug Resistance)	X		X		Samples stored and tested retrospectively if needed (ie, exploratory analyses for subjects if deemed clinically relevant)
Intensive PK sample collection		X			Use of PK Tools for data collection recommended. See Section 5.5.1 for requirements
Sparse PK sample collection			WK 4, 8, 12, 16, 24		See Section 5.5.2 for requirements
Bone Biomarkers (PINP and CTX)	X		WK 12 and 24/ET		Serum collection
Renal Biomarkers (β2-microglobulin and creatinine)	X		WK 48 and 96/ET		Urine collection
Backup Serum and Plasma Sample	X		X		Samples stored and tested if needed

Table 5.1-2: Short-term Procedural Outline (AI468048)

Procedure	In-clinic Visit Day 1	In-Clinic Visit Optional Week 2 for Intensive PK (Day 12-16)	In-Clinic Visits Weeks 4, 8, 12, 16, 24, 32, 40, 48, 60, 72, 84, 96, and/or Early Termination (ET) (± 5 days)	Phone Visits Weeks 20, 28, 36, 44, 54, 66, 78, 90 (± 5 days)	Notes
Outcomes Measures					
EQ-5D-3L Form	X		WK 12, 24, 32, 40, 48, 60, 72, 84, 96		Health Outcomes Questionnaire
FAHI Form	X		WK 12, 24, 32, 40, 48, 60, 72, 84, 96		Functional Assessment of HIV Infection
Clinical Drug Supply					
Call IVRS to Randomize	X				
Dispense Study Drug	X		X		There is no dispensation at Week 96 or ET.

5.1.1 Retesting During Screening or Lead-in Period

Retesting of laboratory parameters and/or other assessments within any single Screening or Lead-in period will be permitted (in addition to any parameters that require a confirmatory value). The Screening Period for this study is 42 days.

Any new result will override the previous result (ie, the most current result prior to Randomization) and is the value by which study inclusion will be assessed, as it represents the subject's most current, clinical state.

Laboratory parameters and/or assessments that are included in [Table 5.1-1](#), Screening Procedural Outline may be repeated in an effort to find all possible well-qualified subjects. Consultations with the Medical Monitor may be needed to identify whether repeat testing of any particular parameter is clinically relevant (eg, a previously failed inclusion criterion).

Rescreening is different than Retesting. Rescreening is the process of Re-enrollment and requires that all procedures be repeated in an entirely new screening period. Rescreening will also be allowed. If it is clinically reasonable, and upon Investigator assessment (and in consultation with the BMS Medical Monitor, if necessary), a subject may be rescreened multiple times during the entire course of the enrollment period. Therefore, subjects may be Rescreened, if, in the opinion of the Investigator, a current clinical outlook of the subjects seems favorable for study inclusion (and if the patient never received study medication in this trial).

The assigned patient identifier (PID) for the subject must be Screen Failed in the IVRS. A new call must be made to the IVRS for the assignment of a new PID for the subject, and all Screening parameters must be done again in reference to the new PID (See [Section 3.3.1](#), Inclusion Criteria 2f). Subject must also be re-consented with the new PID.

5.2 Study Materials

The sponsor will provide each investigative site with the following:

- BMS-955176 Investigator Brochure (IB) and any relevant safety addenda or updates
- Protocol and any Amendments to the Protocol
- Instructions for completing electronic Case Report Forms (eCRFs)
- Laboratory Manual from the central laboratory
- ECG Machines and manual
- IVRS Worksheets to complete when calling the IVRS center to enroll, randomize, and discontinue subjects
- Patient-reported Outcomes Questionnaires: EQ-5D-3L Health Outcome Questionnaire, FAHI (Functional Assessment of HIV Infection)
- PK Tools/Job Aids that may be used for detailed instruction about the PK visits, and as a comprehensive source for documents of date/times of dosing and blood sampling
- Dosing Diaries
 - Completion by subjects is required

- Should include daily dose of study medications administered by subject, modified or missed
- Site staff should review the diaries with the subject at each visit, and, in combination with detailed questioning, should be able to provide comprehensive information in the case report form, noting discrepancies in the subject's file. Dosing Diaries should be maintained in the subject's study file.

5.3 Safety Assessments

The investigative team should follow the protocol-specified schedule of safety-related measurements. Only data for the procedures and assessments specified should be submitted to BMS on the case report form. Additional procedures and assessments may be performed as part of standard of care, however, data for these assessments should remain in the subject's medical record and should not be submitted to BMS, unless specifically requested (ie, as part of an SAE).

5.3.1 *Vital Signs and Physical Examinations*

The schedule of vital signs, physical examinations, and targeted physical examinations is provided in [Section 5.1](#) (Flow Chart/Time and Events Schedule). Vital signs include heart rate, blood pressure, respiration rate, and temperature and should be measured after the subject has been sitting/resting for at least 5 minutes. Physical measurements include height and weight. Targeted physical examinations will include examination of the heart, lungs, skin, abdomen, any symptomatic organ system, and general appearance.

5.3.2 *Adverse Events*

Subjects will be closely monitored throughout the study for any new or ongoing HIV-related diagnoses ([Appendix 2](#)) and/or adverse events. CDC Class C events that occur from the Screening Visit through Day 1 (prior to dosing), will be recorded as Pre-treatment Events. All events that occur after dosing on Day 1 will be recorded on the appropriate Adverse Event eCRF. Additional information on Adverse Events is provided in [Section 6](#).

5.3.3 *Concomitant Medication Assessment*

All medications taken from the Screening Visit throughout the duration of the study will be reported. In addition, any prior therapy with antiretroviral drugs will be reported (See [Appendix 1](#) for Prohibited and Precautionary Therapies).

5.3.4 *Electrocardiograms*

The schedule of electrocardiograms (ECGs) is provided in Section 5.1 (Flow Chart/Time and Events Schedule). ECG machines will be provided by a central vendor who will also perform the read/interpretation of the output.

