3.1.3 Week 2 Intensive PK Visit

Subjects with anemia, defined as Hemoglobin < 11.0 g/dL, should be excluded from participation in the Week 2 Intensive PK Substudy.

Subjects in all arms will have the opportunity to participate in an elective Intensive PK Substudy visit at Week 2 (window for visit: Day 12-16). Approximately 60 subjects, 12 subjects from each arm, are expected to participate in the substudy; BMS may allow the substudy to over-enroll in an effort to have a sufficient number of complete datasets.

The series of 12 blood draws begins with pre-dose (0-hour) blood samples to be collected approximately 24 hours (20-28 hrs) after the morning doses of study drugs that were taken on the day before. Ten more samplings are drawn through the 12-hr time point, with one final sampling collected at the 24-hr time point, requiring the subject to either remain overnight in the clinic, or to return the next morning; the final 24-hr sample will be collected prior to administration of the morning doses of study drugs (See [Section 5.5.1](#)).

PK Tools/Job Aids will be provided to assist with the proper sequencing of dosing and blood sample collections, as well as the collection of required data.

3.1.4 Visits Week 4 - 96

Subjects are expected to be treated for the duration of 96 weeks. In each Stage, after Day 1 and the optional Intensive PK visit at Week 2, subjects will be required to attend 12 more in-clinic study visits over the 96-week treatment period, as follows:

- Visits are conducted every 4 weeks from Week 4 through Week 16
- Visits are conducted every 8 weeks from Week 24 through Week 48
- Visits are conducted every 12 weeks from Week 60 through Week 96

Visits should be scheduled as an interval from the Day 1/Randomization date, and within a window of 5 days earlier or later.

Visits Week 4 - 24 should be conducted in the morning so that the blood is drawn as a pre-morning (pre-AM) dose collection, in order to meet the requirement for Sparse PK (see [Section 5.5.2](#)). One of these visits should meet the very specific timing requirements as outlined in Section 5.5.2.

Telephonic visits will be conducted with each subject at visit Weeks 20, 28, 36, 44, 54, 66, 78, and 90 to conduct an adherence assessment and to continue retention efforts

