3.1.3 Week 2 Intensive PK Visit

Subjects with anemia, defined as Hemoglobin < 11.0 g/dL, should be excluded from participation in the Week 2 Intensive PK Substudy.

Subjects in all arms will have the opportunity to participate in an elective Intensive PK Substudy visit at Week 2 (window for visit: Day 12-16). Approximately 60 subjects, 12 subjects from each arm, are expected to participate in the substudy; BMS may allow the substudy to over-enroll in an effort to have a sufficient number of complete datasets.

The series of 12 blood draws begins with pre-dose (0-hour) blood samples to be collected approximately 24 hours (20-28 hrs) after the morning doses of study drugs that were taken on the day before. Ten more samplings are drawn through the 12-hr time point, with one final sampling collected at the 24-hr time point, requiring the subject to either remain overnight in the clinic, or to return the next morning; the final 24-hr sample will be collected prior to administration of the morning doses of study drugs (See [Section 5.5.1](#)).

PK Tools/Job Aids will be provided to assist with the proper sequencing of dosing and blood sample collections, as well as the collection of required data.

3.1.4 Visits Week 4 - 96

Subjects are expected to be treated for the duration of 96 weeks. In each Stage, after Day 1 and the optional Intensive PK visit at Week 2, subjects will be required to attend 12 more in-clinic study visits over the 96-week treatment period, as follows:

- Visits are conducted every 4 weeks from Week 4 through Week 16
- Visits are conducted every 8 weeks from Week 24 through Week 48
- Visits are conducted every 12 weeks from Week 60 through Week 96

Visits should be scheduled as an interval from the Day 1/Randomization date, and within a window of 5 days earlier or later.

One of the visits Week 4 - 24 should meet the very specific timing requirements as outlined in [Section 5.5.2](#) for a pre-AM dose blood collection.

Telephonic visits will be conducted with each subject at visit Weeks 20, 28, 36, 44, 54, 66, 78, and 90 to conduct an adherence assessment and to continue retention efforts

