Procedure	In-clinic Visit Day 1	In-Clinic Visit Optional Week 2 for Intensive PK (Day 12-16)	In-Clinic Visits Weeks 4, 8, 12, 16, 24, 32, 40, 48, 60, 72, 84, 96, and/or Early Termination (ET) (± 5 days)	Phone Visits Weeks 20, 28, 36, 44, 54, 66, 78, 90 (± 5 days)	Notes
Eligibility Assessments					
Inclusion/Exclusion Criteria	X				
Non-Laboratory Safety Assessments					
Full Physical Examination			WK 12, 24, 48, 96/ET		See Section 5.3.1 for requirements
Targeted Physical Examination	X		WK 4, 8, 16, 32, 40, 60, 72, 84		See Section 5.3.1 for requirements
Vital Signs & Physical Measurements	X		X		See Section 5.3.1 for requirements
Adherence Assessments			X	X	Including review of Dosing Diaries
Pre-treatment Events	X				See Table 5.1-1
Adverse Events Assessments	X	X	X		Serious and Non-serious AEs
Concomitant Medications	X	X	X		See Section 5.3.3
ECG	X		WK 4, 12, 24, 48, 96/ET		See Section 5.3.4 for requirements
Pregnancy Test	X	X	X		For females under age 55, an FSH level must be on record to confirm she is not a WOCBP if pregnancy testing is not being performed. If positive urine, request serum hCG quant. on lab requisition.

Table 5.1-2: Short-term Procedural Outline (AI468048)

Procedure	In-clinic Visit Day 1	In-Clinic Visit Optional Week 2 for Intensive PK (Day 12-16)	In-Clinic Visits Weeks 4, 8, 12, 16, 24, 32, 40, 48, 60, 72, 84, 96, and/or Early Termination (ET) (± 5 days)	Phone Visits Weeks 20, 28, 36, 44, 54, 66, 78, 90 (± 5 days)	Notes
Provide WOCBP with Home Pregnancy test kit(s) to be used during the in-clinic visit interval			WK 16, 24, 32, 40, 48, 60, 72, 84		Provide One Kit at Weeks 16 - 40 Provide Two Kits at Weeks 48 - 84 WOCBP subjects perform test Q4 weeks at home and report results to site.
Laboratory Assessments for Safety and Efficacy and Other Endpoints					
Fasting Chemistry	X		X		Fasting overnight
Fasting Lipid Panel	X		WK 4, 12, 24, 48, 96/ET		Fasting overnight
Hematology	X		X		
Urinalysis	X		X		
Fractional Excretion of Phosphorous (FePO4) (Urine creatinine and phosphorus, Serum creatinine and phosphorus)	X		WK 48 and 96/ET		
Plasma HIV-1 RNA	X	X	X		If collecting an HIV-1 RNA at an UNSCHEDULED visit, also collect samples for Resistance and Exploratory Resistance Testing
CD4 and CD8 T-cell counts	X		X		
HBV Surface Antigen			WK 48 and 96/ET		
HCV Serology			WK 48 and 96/ET		Positive HCV Ab will reflex to HCV RNA

Table 5.1-2: Short-term Procedural Outline (AI468048)

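### The eight phone visits carry no scheduled enquiry about adverse events or concomitant medication, so scheduled enquiry is 8 and later 12 weeks apart although a call already falls in each of those intervals

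*Protocol*

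**What the plan says.** The references are to Revised Protocol 01; the original protocol has the same schedule and wording on this point.

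- **Clinic visits.** Section 3.1.4: after Day 1 and the optional Week 2 visit, "subjects will be required to attend 12 more in-clinic study visits over the 96-week treatment period". They fall every 4 weeks to Week 16, every 8 weeks to Week 48 and every 12 weeks to Week 96.
- **Phone visits.** Calls are set for Weeks 20, 28, 36, 44, 54, 66, 78 and 90. Section 3.1.4 gives their purpose: "to conduct an adherence assessment and to continue retention efforts".
- **Table 5.1-2.** Only the adherence row, annotated "Including review of Dosing Diaries", is marked in the phone column. The adverse-event row, annotated "Serious and Non-serious AEs", and the row "Concomitant Medications" are marked for Day 1, optional Week 2 and the clinic visits, and are blank for the calls.
- **Home pregnancy tests.** One kit is handed out at each of Weeks 16 to 40 and two at each of Weeks 48 to 84. The note reads: "WOCBP subjects perform test Q4 weeks at home and report results to site".
- **Monitoring statement.** Section 5.3.2 opens with "Subjects will be closely monitored throughout the study for any new or ongoing HIV-related diagnoses"; the sentence goes on to cover adverse events.

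**The concern.** The site speaks to every subject between clinic visits from Week 16 onwards, but the schedule does not have it ask about symptoms or new medicines. Section 5.3 tells sites to follow the scheduled safety assessments, so it is unsafe to assume they will ask anyway. In an open-label trial with no data monitoring committee, adverse-event capture between visits is passive.

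Three of the protocol's own statements give this weight.

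- **Gastrointestinal toxicity.** Section 1.5 describes the animal stomach findings as dependent on dose and duration, and gives exposure multiples of 2 and 1 at 120 and 180 mg. The Phase 1 and Phase 2a studies it summarises gave multiple doses for at most 28 days. Here treatment lasts 96 weeks, and scheduled enquiry is sparsest in the second half.
- **Acid reducers.** Appendix 1 prohibits antacids, H2 antagonists and proton pump inhibitors because they may lower atazanavir concentrations, and some antacids may lower dolutegravir. Arms 3 and 4 use unboosted atazanavir, for which Section 1.1.3 acknowledges a risk of subtherapeutic exposure. A subject treating dyspepsia from the pharmacy shelf may not be asked about it for up to 12 weeks.
- **Pregnancy.** The protocol calls BMS-955176 a selective developmental toxicant. Reporting within 24 hours can start only once the site knows of the pregnancy.

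At stake are later detection and longer recall. The primary endpoint, HIV-1 RNA at Week 24, is untouched.

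**Working it through.** **Inputs** (Table 5.1-2 and Section 3.1.4)

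- Clinic visits: Weeks 4, 8, 12, 16, 24, 32, 40, 48, 60, 72, 84, 96. The count is 12, which reproduces the figure in Section 3.1.4.
- Calls: Weeks 20, 28, 36, 44, 54, 66, 78, 90. The count is 8.
- Window: 5 days either side of each visit.

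**Step 1. Gaps between scheduled enquiries as written** (clinic only)

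| Period | Intervals | Nominal gap | Longest gap with windows | Calls in each interval |
|---|---|---|---|---|
| Weeks 0–16 | 4 | 4 weeks | 4 × 7 + 10 = 38 days | 0 |
| Weeks 16–48 | 4 | 8 weeks | 8 × 7 + 10 = 66 days | 1 |
| Weeks 48–96 | 4 | 12 weeks | 12 × 7 + 10 = 94 days | 1 |

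The 12-week gaps cover 4 × 12 = 48 of the 96 weeks.

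**Step 2. Gaps if the existing calls carry the enquiry**

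- Post-baseline enquiries: 12 + 8 = 20 (optional Week 2 excluded from both counts).
- Weeks 16–48: each call falls midway, so 8 weeks becomes 4.
- Weeks 48–96: each call falls midway, so 12 weeks becomes 6. With windows, 6 × 7 + 10 = 52 days against 94.

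**Step 3. Home pregnancy tests**

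Kits: 4 × 1 (Weeks 16, 24, 32, 40) + 4 × 2 (Weeks 48, 60, 72, 84) = 12. Counting every 4 weeks from the clinic visit at which the kit is given:

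| Tests due at Weeks | Next contact if the calls prompt for results | Delay |
|---|---|---|
| 20, 28, 36, 44 | call in the same week | 0 weeks |
| 52, 64, 76, 88 | calls at Weeks 54, 66, 78, 90 | 2 weeks |
| 56, 68, 80, 92 | clinic visits at Weeks 60, 72, 84, 96 | 4 weeks |

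So 4 + 4 = 8 of the 12 tests gain a call. The other 4 fall after the only call in their interval and are next met in clinic, as now.

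**The case against.** The case for leaving the schedule alone is substantial, and much of it stands.

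- **Capture is not confined to prompts.** Section 6 allows spontaneous reports, Section 6.2.1 requires every identified nonserious event to be recorded, and Section 5.3.3 requires all medication throughout the study to be reported. A reader might infer from the blank cells that events between visits go unrecorded. They do not show that: an event mentioned on a call must be recorded, and the next clinic visit asks again. What is missing is the question.
- **Tapering is intended.** Section 1.5 says examinations and laboratory tests are more frequent initially, and the visit pattern matches. A reader might take the wide gaps as breaking the close-monitoring statement in Section 5.3.2. That statement sets no frequency, so nothing is contradicted.
- **Pregnancy results are not left uncollected.** A reader might infer that home results go unseen for up to 12 weeks, or reach the site only by goodwill. Table 5.1-2 instructs women to report them and also schedules a pregnancy test at every clinic visit. Only the absence of a named contact for chasing an unreported result survives.
- **It is a design preference.** Only one interval up to Week 24 (Weeks 16–24) contains a call, the 12-week gaps start after Week 48, and the calls have a legitimate purpose in adherence and retention. This limits the importance of the point. It does not explain why a call already being made, which Section 4.7 counts among the contacts at which subjects are interviewed about adherence, should omit two standard questions.

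**Conclusion.** The point holds as a weakness in the assessment schedule. No adverse-event or concomitant-medication enquiry is scheduled at any of the eight calls, which leaves four nominal gaps of 8 weeks and four of 12. Using the existing calls would halve each of them. For pregnancy the gain is a backstop to a reporting instruction that already exists, and it reaches 8 of 12 home tests.

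The conclusion assumes that blank cells mean no scheduled enquiry, as Section 3.1.4 supports, and that home tests run every 4 weeks from the clinic visit at which the kit is given. The documents give no figure for how many events or medicines would be detected sooner, so the benefit is stated only as shorter intervals. It is worth making because it is cheap; it does not bear on the validity of the efficacy results.

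**What to change.** In Table 5.1-2, mark the phone column for adverse-event assessment and for concomitant medication. Ask open-ended questions, as Section 6 requires, covering serious and nonserious events. Add a prompt at the calls for any home pregnancy result not yet reported, and extend the stated purpose of the calls in Section 3.1.4 to match. Apply this identically in all five arms so that ascertainment does not differ by treatment.

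This changes data collection only; it alters no dose, treatment or discontinuation rule.

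The cost is a wording amendment, a short call script and use of the existing case report form pages. No contact, visit or test is added. Calls will run a few minutes longer, and somewhat more low-grade events will be recorded in every arm. If the change takes effect after Stage 1 subjects have passed Week 16, its date should be recorded, because event frequencies in the two stages would then rest on different enquiry schedules.
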